They have another Axis I disorder as a principal diagnosis in the 6 months prior to screening;
They have a history of substance abuse or dependency in the 2 months prior to screening;
Pregnant women, lactating women, and women of childbearing potential not using medically accepted forms of contraception;
Patients with current or recent suicidality;
Scoring 10 or greater on the BDI
Scoring 2 or greater on the suicide question of the BDI
Psychotic disorders, bipolar disorder;
They are considered to be at a significant risk of committing homicide;
They have an unstable medical condition;
Women of childbearing potential (WOCBP) who are pregnant or are considering becoming pregnant during the length of the study;
They are regarded, for any reason by the principal investigator as being an unsuitable candidate for the protocol.
There has been a change in their medication or psychotherapy treatment regimen in the month preceding screening;

Mode of Administration: Patients will be randomly assigned to the active group or control group in a 1:1 ratio. Patients in the control group will be injected with a saline solution. Patients in the active group will receive 40 units of Botox (females) or 50 units (males). For females, 8 units will be injected into the procerus and 8 units into both the right and left medial and lateral corrugators. For males, 10 units will be injected into each location.

Method of Blinding: This will be a double-blind study. The clinician administering the injections will be blinded. After the initial visit, to help maintain the blind, all data will be collected via a web portal with online questionnaire assessments.

Duration of Treatment: The study will be divided into three phases: screening and enrollment, treatment, and follow-up. Patients who meet all criteria will be randomized at the screening visit. The follow-up phase will last eight (8) weeks after the investigational product is administered. Patients will be instructed to complete the LSAS and BDI online at week 4 and 8.

General Design and Methodology: Prior to screening, potential participants will fill out the LSAS and BDI online in order to determine initial eligibility. Those who meet the criteria will be

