scheduled for an in-person screening visit. At screening, patients will sign consent and be diagnosed by means of the MINI (Sheehan et al,1998) , and will have a DSM-IV diagnosis of Social anxiety disorder (SAD). They will complete the LSAS. They will also complete the patient-rated BDI (Beck et al.,1961). Patients who meet all criteria will be randomly assigned to receive either the investigational product or placebo. Patients will be photographed, at the initial visit, at rest. The study medication or placebo will be injected within 7 days of clinical assessments into the procerus and corrugator supercilii frown muscles of each patient by a physician's assistant who is experienced in the administration of this medication. Four weeks \pm 7 days, and eight weeks \pm 7 days following the injection, each patient will complete online assessments. Patients will complete online the adverse events (AEs) and concomitant medications questionnaires will be at week 4 and 8.

Investigational New Drug (IND) Application: This study is exempt from the requirement for an IND submission based on the following criteria: Botox is lawfully marketed in the United States. There is no intent to report the findings of this trial to the FDA in support of a new indication or any significant change in the labeling of the drug. This study is not intended to support a significant change in the advertising of the prescribed drug. Compared to the current labeling of Botox, there will be no change in the route of administration, the dosage level, or any other factor that significantly increases the risk, or decreases the acceptability of the risk, associated with the use of the drug. Botox is approved for doses up to 400 units. We will use 40 or 50 units. The patient population will be different compared to the current labeling, which specifies bladder dysfunction, chronic migraine, upper limb spasticity, cervical dystonia, blepharospasm, strabismus and primary axillary hyperhidrosis. The change in population will not significantly increase the risk. All participants in the study will be medically stable adults.

BACKGROUND INFORMATION

Introduction

Investigational Treatment

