The use of botulinum toxin A to correct glabellar frown lines is an effective and popular cosmetic procedure with more than 1 million treatments per year in the United States alone (Carruthers, A.). Botulinum toxin type A marketed commercially as BOTOX® Cosmetic (Botox), is produced from fermentation of Hall strain Clostridium botulinum type A grown in a medium containing casein hydrolysate, glucose, and yeast extract, intended for intramuscular use. It is purified from the culture solution by dialysis and a series of acid precipitations to a complex consisting of the neurotoxin, and several accessory proteins. The complex is dissolved in sterile sodium chloride solution containing Albumin Human and is sterile filtered (0.2 microns) prior to filling and vacuum-drying. Each vial of Botox contains 100 Units of Clostridium botulinum type A neurotoxin complex, 0.5 mg of Albumin Human, and 0.9 mg of sodium chloride in a sterile, vacuum-dried form without a preservative.

Botox blocks neuromuscular transmission by binding to acceptor sites on motor nerve terminals, entering the nerve terminals, and inhibiting the release of acetylcholine. This inhibition occurs as the neurotoxin cleaves SNAP-25, a protein integral to the successful docking and release of

acetylcholine from vesicles situated within nerve endings. When injected intramuscularly at therapeutic doses, Botox produces partial chemical denervation of the muscle resulting in a localized reduction in muscle activity. In addition, the muscle may atrophy, axonal sprouting may occur, and extrajunctional acetylcholine receptors may develop. There is evidence that reinnervation of the muscle may occur, thus slowly reversing muscle denervation produced by Botox.

Botox is indicated for the temporary improvement in the appearance of moderate to severe glabellar lines associated with corrugator and/or procerus muscle activity in adult patients ≤ 65 years of age.

Botox is contraindicated in the presence of infection at the proposed injection site(s) and in individuals with known hypersensitivity to any botulinum toxin preparation or to any of the components in the formulation.

Findings from Non-clinical and Clinical Studies

Glabellar Lines

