However, adverse effects are dependent upon the site of injection. No definitive serious adverse event reports of distant spread of toxin effect associated with dermatologic use of Botox for glabellar lines have been reported. Similarly, no definitive serious adverse event reports of distant spread of toxin effect associated with Botox for blepharospasm at the recommended dose or for strabismus at the labeled doses have been reported.

Hypersensitivity Reactions

Serious and/or immediate hypersensitivity reactions have been reported. These reactions include anaphylaxis, urticaria, soft tissue edema, and dyspnea. One fatal case of anaphylaxis has been

reported in which lidocaine was used as the diluent, and consequently the causal agent cannot be reliably determined.

Pre-Existing Neuromuscular Disorders

Patients with neuromuscular disorders may be at increased risk of clinically significant effects including severe dysphagia and respiratory compromise from typical doses of Botox.

Human Albumin

This product contains albumin, a derivative of human blood. Based on effective donor screening and product manufacturing processes, it carries an extremely remote risk for transmission of viral diseases. A theoretical risk for transmission of Creutzfeldt-Jakob disease (CJD) also is considered extremely remote. No cases of transmission of viral diseases or CJD have ever been identified for albumin.

PURPOSE OF THE STUDY AND STUDY OBJECTIVES

Purpose of the Study

The purpose of the study is to evaluate the efficacy of botulinum toxin A as a treatment for SAD.

Study Objectives

The primary objective of this proposed study is to obtain data on the efficacy of Botox in reducing symptoms of SAD in male and female patients between the ages of 18 and 65 years old.

Efficacy will be determined by using a continuous measure of outcome, the Self Rated Liebowitz Social Anxiety Scale (Fresco et al, 2001) and dichotomous indicators of response (LSAS < 50) and remission (LSAS < 30).

Patients will also be assessed with the self-rated version of the BDI at screening, 4 weeks, and 8 weeks.

STUDY DESIGN

The study will begin in May 15, 2016 and be completed by September 2017. Approximately 30 patients will be randomized and enrollment will be complete when that number is reached. It is estimated that up to 100 patients will have to be screened in order to randomize 30.

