Potential participants will begin by going to REDCap, a mature, secure web application for building and managing online surveys and databases, and providing basic demographic information (age, sex, and employment status). They will then complete the LSAS and BDI on REDCap. If they meet the inclusion criteria, they will be asked for their name, telephone number, and email address, and a screening visit will be scheduled for an in-person screening appointment. If they do not, they will be provided with a list of referrals where they can obtain

clinical treatment. No identifiable information will be collected from these people. Their anonymous data will be used to compare the characteristics of those who met the criteria for participation, and those who did not. This information is routinely requested by journal editors in order to help readers evaluate the generalizability of the results.

At screening, patients will be asked to give consent, and the MINI diagnostic interview will be administered by a study coordinator with extensive experience administering the MINI and other psychiatric scales. The diagnosis will be confirmed by a clinical interview with the principal investigator, a board certified psychiatrist. He will also collect information on concomitant medications, and review the inclusion exclusion criteria with the potential participant. The PI will also evaluate the stability of the patient, comorbid medical and psychiatric conditions, and safety considerations such as the presence of suicidal ideas. WOCBP will be asked to take a urine pregnancy test.

People who decline to consent, or don't meet the inclusion/exclusion criteria, will be provided with a list of referrals where they can obtain clinical treatment. If the person is in crisis, the crisis will be managed by the PI. If they will not be in the study, all of their identifying information will be destroyed. The anonymous data will be kept as described above. If they don't come to the screening visit, an attempt will be made to reschedule it. If it is not successfully rescheduled, the identifying information will be destroyed. Participants who meet all criteria will be photographed, and randomly assigned to receive either the investigational product or placebo (saline).

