All procedures except photography and administration of investigational product will take place in the clinical offices of GWU MFA. For photography and administration of the investigational product, patients will be transported by taxi or private car service to the Chevy Chase Cosmetic Center, located at [name]. After the study procedures are complete, participants will be transported back to GWU MFA or to a nearby Metro station, if they prefer.

The injectable syringes will be prepared by [name] at the Chevy Chase Cosmetic Center. Syringes will contain either Botox or saline based on the randomization scheme. They will be marked with numbers written on tape affixed to clear envelopes that contain only the individual syringes. After being made, syringes will be stored in a refrigerator at 4 degrees Celsius in the Chevy Chase office. All patients will be examined and injected by a physician assistant, [name], who has been trained in the practice of injection, and was the injector for the Finzi and Rosenthal clinical trial studying Botox for the treatment of major depressive disorder. [name] will have no contact with patients, to maintain the blind.

The study medication or placebo will be injected into the procerus and corrugator supercilii frown muscles of each patient by a physician or physician's assistant.

Four and eight weeks following the injection, patients will be contacted and asked to complete the online LSAS and BDI self-assessments as well as reporting on concomitant medications and adverse events.

Participants will receive a gift card for up to \$45 at the completion of the study. They will receive \$25 if they complete the screening visit, and additional \$10 if they complete the first post-treatment online assessment, and another \$10 if they complete the second post-treatment online assessment.

Safety Measures

Adverse events will be collected via online assessments, and will be reviewed by the investigator within 24 hours. Patients will be contacted by telephone, or asked to come in for a face-to-face meeting if the investigator believes that the patient is at risk or if further evaluation of the adverse event is needed. Patients will be instructed to contact the investigator by telephone at any time if they have concerns about adverse events they may be experiencing.

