The effect of administering different botulinum neurotoxin serotypes at the same time or within several months of each other is unknown. Excessive neuromuscular weakness may be exacerbated by administration of another botulinum toxin prior to the resolution of the effects of a previously administered botulinum toxin.

Stopping Rules and Discontinuation Criteria

A participant may discontinue participation in the study at any time for any reason (e.g., lack of efficacy, consent withdrawn, or adverse event). The investigator may discontinue a patient from the study at any time for any reason (e.g. non-adherence to the protocol, emergence of psychiatric instability).

Confidentiality and Privacy Regarding Participants

The investigator will assure the privacy of all patients, including their personal identity and all personal medical information at all times. Data will be stored on the secure REDCap system or on a password-protected computer in a locked office. Hard copies of data will be stored in a locked office, and destroyed after the data is entered into a computer. Participants will be assigned a code number, and all data will be identified by this code. The code key will be kept separate from the data, and will be destroyed five years after publication of the study results. Photographs of the participants will be altered to eliminate the possibility of identification five years after publication of the study results. This will entail cropping out the entire face except for the area that was injected. The retained image will not include the participants' eyes, or any features below the eyes. The remaining, fully anonymized data will be kept indefinitely. Privacy will be assured by conducting all in-person procedures in private clinical offices or exam rooms.

Conflict of Interest

[name], PhD, a sub-investigator on the study, holds a patent on the use of Botox for social anxiety disorder. The conflict of interest will be managed in the following way: [name] will prepare the investigational product according to the randomization scheme. He will have no contact with participants. He will not collect or analyze data. The principal investigator, who has no conflict of interest, will approve all manuscripts prior to submission and publication.

REFERENCES

Carruthers A. Botulinum toxin type A: history and current cosmetic use in the upper face. *Dis Mon* 2002; 48: 299.

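### The protocol warns that Botox may endanger patients with neuromuscular disorders, but no exclusion criterion names them, so keeping out a patient with stable disease rests on judgement

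*Combined protocol and SAP*

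**What the plan says.** Under Pre-Existing Neuromuscular Disorders, within the section on known and potential risks, the protocol states: "Patients with neuromuscular disorders may be at increased risk of clinically significant effects including severe dysphagia and respiratory compromise from typical doses of Botox". The sentence does not depend on whether the disorder is stable.

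The Criteria for Exclusion in the protocol summary cover earlier botulinum toxin treatment, psychiatric diagnoses and scores, substance use, suicide and homicide risk, pregnancy and lactation, and recent treatment changes. Two broader items follow. One is medical: "They have an unstable medical condition". The other is discretionary: "They are regarded, for any reason by the principal investigator as being an unsuitable candidate for the protocol". Neuromuscular disease appears nowhere in the list.

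The Investigational New Drug (IND) Application section also reasons from stability: "The change in population will not significantly increase the risk. All participants in the study will be medically stable adults".

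Three other provisions bear on the point. Study Design says of screening: "The PI will also evaluate the stability of the patient, comorbid medical and psychiatric conditions". It says of the injection visit: "All patients will be examined and injected by a physician assistant". Stopping Rules and Discontinuation Criteria adds: "The investigator may discontinue a patient from the study at any time for any reason".

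**The concern.** The written medical criterion turns on stability and the warning does not. A person with a known, well-controlled neuromuscular disorder passes the criterion and still belongs to the group the warning describes.

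Patient safety is at stake. The whole dose is given at one visit, so after injection it cannot be reduced or withdrawn. The protocol's own risk text says that effects of toxin spread have appeared from hours to weeks after injection and that swallowing and breathing difficulty can be fatal. The scheduled adverse event questionnaires are online, at weeks 4 and 8. Patients may telephone at any time, but no earlier safety contact is planned. Prevention therefore has to happen before the needle, and it happens only if someone identifies the disorder and decides to exclude.

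**Working it through.** The plan gives no figure to reproduce. The check is a reading of the eligibility text against the warning, followed by an illustrative bound on size.

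**Step 1. Follow one patient through the text.** Take an applicant who qualifies on social anxiety, has a low depression score and has a known, stable neuromuscular disorder.

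- Inclusion criteria: nothing concerns neuromuscular or general medical status, so the applicant passes.
- Named exclusions: none applies.
- Unstable medical condition: does not apply, because the disease is stable.
- Population statement in the IND section: the applicant fits it.
- Warning in the risk section: applies in full.

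**Step 2. Ask of each safeguard whether it requires exclusion.**

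| Safeguard | Where | Names the disorder? | Requires exclusion? |
|---|---|---|---|
| Investigator's review of comorbid conditions | Study Design, before randomisation | No | No |
| Unsuitable for any reason | Criteria for Exclusion | No | Only if the investigator so judges |
| Physician assistant's examination | Study Design, at the injection site | No; content not stated | No |
| Discontinuation by the investigator | Stopping Rules | No | No |

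Each can catch the patient, but none must. The third comes after randomisation, which takes place at the screening visit.

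**Step 3. Check whether enrolment would breach the protocol.** Investigational Treatment gives the contraindications: "Botox is contraindicated in the presence of infection at the proposed injection site(s) and in individuals with known hypersensitivity". Neuromuscular disorder is not among them. The protocol thus treats it as a precaution, and enrolling the patient would break no rule.

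**Step 4. Bound the size.**

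Inputs from the protocol: about 30 patients randomised (Study Design), in a 1:1 ratio (Mode of Administration), so 30 / 2 = 15 receive toxin.

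Assumption, not in the documents: a proportion p of otherwise eligible applicants have a known stable neuromuscular disorder, and no safeguard catches any of them.

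P(at least one of 15 exposed) = 1 − (1 − p)^15

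- p = 1 in 10,000: 1 − 0.9999^15 = 0.15%
- p = 1 in 1,000: 1 − 0.999^15 = 1.5%
- p = 1 in 100: 1 − 0.99^15 = 14.0%

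The assumed range spans a factor of 100, so these figures show scale only.

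**Step 5. Put the dose in context.** The study gives 40 units to women and 50 to men. The phase 3 trials described under Glabellar Lines used 20 units in healthy adults, so the ratios are 40 / 20 = 2.0 and 50 / 20 = 2.5. Against the 400 units cited in the IND section, they are 40 / 400 = 10% and 50 / 400 = 12.5%. The warning refers to typical doses, so a dose within the approved range does not answer it.

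**The case against.** The strongest reply is that the protocol already deals with this sensibly. A board certified psychiatrist must look at comorbid conditions and safety before randomisation and may turn away anyone. A trained injector then examines every patient, and both work from a protocol that contains the warning. A patient who would report a known disorder when asked is also the one a comorbidity review is most likely to find, so the gain from a named criterion is small. That stands, and it limits the weight of the point.

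Second, the protocol manages a neighbouring risk the same way. The section on concomitant therapy advises caution, not prohibition, for drugs that interfere with neuromuscular transmission. Treating the disorder as a precaution is consistent with that and with the contraindications. This also stands: the plan does not contradict itself.

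Third, the risk section says that adverse effects depend on the injection site, links effects beyond that site to some cases of higher doses, and reports no definitive serious distant-spread events in glabellar use. This lowers concern. It does not remove it, because the statement about glabellar use does not mention neuromuscular patients and the phase 3 glabellar trials enrolled healthy adults.

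Fourth, the IND text compares the trial population with the labelled indications and is not an eligibility rule. That is fair. It is cited here only because its reassurance also rests on stability.

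Fifth, the prevalence range is assumed, and the 14% figure needs both its top value and the failure of every safeguard. It is an upper bound under those assumptions, not a forecast. Finally, consent pages and screening forms are not in the text reviewed, so a question about neuromuscular disease may already be asked. That would not supply the missing criterion.

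**Conclusion.** The point holds. The warning is unconditional, no exclusion criterion names the group it covers, and the one general medical criterion admits a patient whose disease is stable. Exclusion is possible at several stages and required at none.

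The likely number affected is few or none of about 15 toxin-treated patients. The illustrative chance of at least one exposure, 0.15% to 14%, rests wholly on an assumed prevalence and on no safeguard working; the investigator's review would lower it. The documents support no estimate of harm. The change is worth making because the potential harm is severe, the dose cannot be taken back and the remedy costs very little. Confidence is medium. It should be made as an improvement to eligibility; it does not affect the validity of the analysis.

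**What to change.** Add known neuromuscular disorder to the Criteria for Exclusion, with examples set by the investigator, and ask about it by name at the screening visit before randomisation. The question fits within the comorbidity review already required. Some judgement remains over which diagnoses count, but any applicant who reports a listed disorder would then be excluded by rule.

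The cost is one line and one question. Sample size, analysis and error rates do not change. The downside is the possible loss of a rare applicant: 100 × p gives 0.01, 0.1 or 1 of up to 100 people screened at the three assumed proportions. This applies p to everyone screened. Since p is defined for otherwise eligible applicants, and only about 30 are enrolled, the loss among people who would have been randomised is nearer 30 × p, or 0.003 to 0.3.

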A Controlled Study of the Efficacy of Botulinum Toxin A (Botox) for the Treatment of Social Anxiety Disorder (SAD)

[name]
[name], PhD

CONTACT INFORMATION

Primary contact:
[name], [contact], [contact]

CLINICAL STUDY PROTOCOL SUMMARY

Sponsor: Dermatology and Cosmetic Surgery Associates, LLC

Investigational Treatment: Five injections of Botox will be administered at a single treatment visit.

Title of Study: A Controlled Study of the Efficacy Botox Treatment for the Treatment of Social Anxiety Disorder (SAD)

Date: 3/8/2016

Number of centers: One

Primary Objective: The objective of this proposed study is to obtain data on the efficacy of Botox in reducing symptoms of social anxiety disorder (SAD) in male and female patients between the ages of 18 and 65 years old. Efficacy will be determined by using a continuous measure of outcome, the Liebowitz Social Anxiety Scale (Primary outcome) (LSAS; Fresco et al, 2001) and dichotomous indicators of response (Primary outcome) (LSAS <50) and remission (Secondary Outcome) (LSAS <30). Subjects will be assessed using: the self-rated LSAS and the self-rated version of the BDI-I at screening, 4 weeks, and 8 weeks.

Statistical Considerations: An ANOVA with repeated measures to determine whether there are statistical differences between the interventions will be used. Because the effect size of the intervention is unknown, the power statistics required to obtain significant differences between placebo and Botox cannot be calculated.

Number of Patients Planned: Up to 100 subjects will be screened in order to enroll 30.

Diagnosis and Criteria for Inclusion: Patients will be included in this study if they meet all of the following criteria:

Written informed consent is obtained;
They are a 18 to 65 years old;

A primary diagnosis for SAD as diagnosed by the MINI, and their current episode must be at least one month in length; A total score on the LSAS of 60 or greater
Women of childbearing potential (WOCBP) are on an acceptable form of birth control and are not pregnant or lactating;
They are judged by the investigator to have the capacity to understand the nature of the study;
They are willing to comply with all the requirements of the study.
They are considered by the investigator to be likely to adhere to the protocol.

Criteria for Exclusion: Patients will be excluded from this study if they meet any of the following criteria:

They have ever been treated with botulinum toxin A ;

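### LSAS is collected twice before randomisation, but the analysis plan names neither score as a covariate and gives the online score no role in the efficacy analysis

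*Combined protocol and SAP*

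**What the plan says.** All references are to the combined protocol and SAP.

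- **Online score.** General Design and Methodology (protocol summary): "Prior to screening, potential participants will fill out the LSAS and BDI online in order to determine initial eligibility". The Study Design section repeats it: "They will then complete the LSAS and BDI on REDCap".
- **Visit score.** General Design and Methodology, on the screening visit: "They will complete the LSAS". The Study Design account of the same visit lists consent, the MINI, the investigator's interview and a pregnancy test, but no LSAS.
- **Efficacy times.** Primary Objective: "Subjects will be assessed using: the self-rated LSAS and the self-rated version of the BDI-I at screening, 4 weeks, and 8 weeks". The online form comes before screening, so it is not among these times.
- **Linkage.** Study Design, straight after the online form: "If they meet the inclusion criteria, they will be asked for their name, telephone number, and email address". For people who go on to randomisation, the online record can therefore be tied to the patient.
- **Other stated use.** Study Design says the anonymous pre-screen data will be used to compare those who met the criteria with those who did not.
- **Analysis.** Statistical Considerations: "An ANOVA with repeated measures to determine whether there are statistical differences between the interventions will be used". Nothing there defines baseline, lists a covariate or names the contrast to be tested.
- **Size.** "Up to 100 subjects will be screened in order to enroll 30", "randomly assigned to the active group or control group in a 1:1 ratio", which gives about 15 per arm.

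**The concern.** Patients enter at LSAS 60 or above and will differ widely in severity. In a comparison of 15 against 15, those differences are a large part of the noise, and a chance imbalance in severity is likely enough to matter. A score taken before randomisation can remove some of that noise without biasing the arm comparison. Selection at 60 and the regression to the mean that follows act alike in both arms.

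The plan collects two such scores and commits to using neither as a covariate. Screening may be meant as one level of the repeated-measures factor, but this is not stated. The choice of baseline is therefore open until the data are in. If the gap were closed with the screening score alone, the online score would still have no role, although the mean of two scores can measure usual severity with less occasion-to-occasion error than one.

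**Working it through.** **1. Inputs.** From the documents: two pre-treatment scores, outcomes at weeks 4 and 8, 30 patients at 1:1, entry at LSAS 60 or above. The documents give no SD, correlation, effect size or power, so there is no planned figure to reproduce. Everything below on size is assumption, shown as a range.

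**2. Closed form, ignoring the entry cut.** Take unit variance and equal correlation ρ between all occasions. The outcome is the mean of weeks 4 and 8. The mean of any two scores has variance v = (1+ρ)/2, and its covariance with any other score is ρ. Residual variance is:

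- no adjustment: v
- screening score as covariate: v − ρ²
- mean of the two scores as covariate: v − ρ²/v

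| ρ | none | screening | mean of two | mean vs screening | mean vs none |
|---|---|---|---|---|---|
| 0.3 | 0.650 | 0.560 | 0.512 | −8.7% | −21% |
| 0.5 | 0.750 | 0.500 | 0.417 | −16.7% | −44% |
| 0.7 | 0.850 | 0.360 | 0.274 | −24.0% | −68% |
| 0.8 | 0.900 | 0.260 | 0.189 | −27.4% | −79% |

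The share of the total reduction that screening alone achieves is ρ² ÷ (ρ²/v) = v, or 65% to 90% here. The first covariate does most of the work.

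If the ANOVA amounts to change from screening, its variance is (1−ρ)(1/2+1). At ρ = 0.5 that is 0.750, no better than no adjustment.

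With 15 per arm, two-sided 5% and 80% power, the detectable difference is (1.96+0.84)·√(2·variance/15). At ρ = 0.5 it is 0.886 SD unadjusted, 0.723 SD with screening and 0.660 SD with the mean of two.

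**3. Allowing for the entry cut, with stable severity.** This was simulated with both pre-treatment scores at 60 or above, applicant mean 60 to 75, between-patient SD 18 to 22, single-score reliability 0.6 to 0.9 and patient-specific change SD 5 to 20. Against screening alone, the mean of two lowers residual variance by 2.7% to 20.4% (week 8 alone: 2.6% to 16.0%).

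A middle case (mean 75, SD 22, reliability 0.8, change SD 10) gives about 13%. It is 13.6% if 22 is the SD of true severity, and 12.6% in a second run, in line with reading 22 as the SD of the observed score. At 13.6%, 30/(1−0.136) = 34.7, so the gain is worth about 5 patients.

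**4. Allowing severity to drift.** The interval between the online form and the visit is not stated, so equal correlation cannot be taken for granted. The same cut was applied with mean 75 and SD 22. The change in residual variance against screening alone (positive is a gain) was:

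| Share of variance: trait / drifting state / noise | Gap | Gain |
|---|---|---|
| 80 / 0 / 20 (no drift, no patient-specific change) | any | +23% |
| 30 / 50 / 20, state correlation 0.9 per week | 1 week | +4.6% |
| same | 4 weeks | +1.5% |
| same | 8 weeks | −1.0% |
| same, online score with extra noise of SD 10 | 4 weeks | −1.3% |
| 40 / 50 / 10, 0.95 per week | 8 weeks | −4.0% |
| pure drift, 0.95 per week | 4 weeks | −12% |

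In a set of such scenarios, adjusting for the mean of two still cut residual variance by 23% to 65% against no adjustment. It also beat change from screening in all but pure drift, where the two were about level (−0.4%). These are scenario results, not bounds: at ρ = 0.3 the table in step 2 already gives 21%.

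**5. How the score enters.** The mean costs one degree of freedom, the same as screening alone. Entering both scores separately costs a second. The approximate variance inflation is 27/26 = 1.038 for one covariate and 27/25 = 1.080 for two, about 4% more.

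Adding the online score as a further level of the repeated-measures factor would hurt a test of the group main effect. A constant treatment effect present at 2 of 3 levels becomes one present at 2 of 4, so it is diluted from 2/3 to 1/2 of its size.

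**The case against.** The strongest case against acting is that one screening baseline is a conventional, valid choice, and that the value of a second score depends on unseen figures. Much of this stands.

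- A reader might infer that the online score is **discarded**. The documents do not say so. Its absence from a one-sentence analysis plan is an omission, not a decision, and Study Design gives the pre-screen data a descriptive use.
- A reader might infer that **every randomised patient certainly gives two scores**. General Design and Methodology supports this, and Primary Objective lists the LSAS at screening. But Study Design does not list an LSAS at the visit, and the sections need aligning.
- A reader might infer a **guaranteed gain** of at least 3%, or one patient. That floor holds only if severity is stable and the two scores are equally reliable. Step 4 shows that the equal-weight mean can lose when the gap is long or the online score is noisier. People also fill in that form to qualify, which is a reason not to assume equal reliability.
- The comparison with screening alone presupposes a covariate adjustment that the plan does not contain. The missing baseline and contrast definition is the larger gap.
- The online form is completed before consent, which is signed at screening. Its use as a linked covariate has to be covered.

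None of this removes the basic point. Pre-treatment LSAS should be a prespecified covariate, and a second score already planned should have a stated rule for its use.

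**Conclusion.** The concern holds as an optional efficiency improvement. Two LSAS scores are planned before randomisation, neither is named as a covariate, and the online score has no stated part in the efficacy analysis. Prespecifying the adjustment is the main benefit.

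The increment from the second score is about 3% to 20% lower residual variance under stable severity (roughly 1 to 8 patients on 30). It is near zero or slightly negative in the mixed drift models, and worse only under pure drift. Correlations, reliability and the interval between the two scores are all assumed.

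A reader might take this as an error that biases the result. It is not one: the arm comparison is valid with or without the second score. Nor does the gain carry over directly to the dichotomous response outcome (LSAS <50).

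**What to change.** Add to Statistical Considerations:

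> The arm comparison of continuous LSAS at weeks 4 and 8 is adjusted for pre-treatment LSAS as a covariate. The covariate is the mean of the online and screening-visit totals when the online form was completed within [N] days before the visit. Otherwise, or when the online total is missing, it is the screening-visit total. Neither score is added as a further level of the repeated-measures factor.

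Fix N before any unblinded data are seen, and keep it short, since step 4 shows the gain fading as the gap grows. The rule uses only information from before randomisation, so it cannot bias the comparison.

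Also:

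- align Study Design with General Design and Methodology on whether the LSAS is completed at the visit;
- keep the online total and its completion date under the patient's code number;
- state in the consent form that the online answers will be used in the analysis.

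The cost is a short paragraph in the plan, one linkage step in REDCap, a line of consent text and any ethics notification that this requires. No new visits, data or patients are needed, and no more degrees of freedom than adjusting for the screening score alone.
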